10.3 Statistical Design

10.3.1 Part A - Determining MTD Using Bayesian Optimal Interval Design

For dose-escalation, the BOIN design (Liu and Yuan, 2015; Yuan et al, 2016) is employed to find the MTD. The BOIN design is implemented in a simple way similar to the traditional 3+3 design,

[figure not shown]
but is more flexible and possesses superior operating characteristics that are comparable to those of the more complex model-based designs, such as the continual reassessment method (CRM) (Zhou et al, 2018).

The target toxicity rate for the MTD is $\phi = 0.3$ and the maximum sample size is 25 (below steps describe the process in detail). To guide dose-escalation decisions, if the observed DLT rate at the current dose is ≤ 0.236 , the next cohort of patients will be treated at the next higher dose level; if it is ≥ 0.359 , the next cohort of patients will be treated at the next lower dose level. For the purpose of overdose control, doses j and higher levels will be eliminated from further examination if $\Pr(p_j > 0.3 | \text{data}) > 0.95$, where p_j is the true DLT rate of dose level $j, j = 1, 8$. When the lowest dose is eliminated, stop the study for safety.

The study design is illustrated in [Figure 10-1](#) below and described through the following 3 steps:

- a) Perform accelerated titration as follows: treat the first patient at dose level 1. If no \geq Grade 2 toxicity (as assessed by the Investigator to be related, probably related, or possibly related to the drug at any dose level) is observed, escalate the dose to the next higher level. Continue this 1-patient-per-dose dose-escalation process until the first \geq Grade 2 toxicity is observed or dose level 5 (80 mg dose level) is reached. Treat an additional 2 patients at the dose at which the first \geq Grade 2 toxicity is observed. Hereafter, patients are treated in cohorts of 3 as described in steps 2 and 3.
- b) To assign a dose to the next cohort of patients, conduct dose-escalation/de-escalation according to the rule displayed in [Table 10-2](#). When using [Table 10-2](#), please note the following:
 - c) “Eliminate” means that we eliminate the current and higher doses from the study to prevent treating any future patients at these doses because they are overly toxic.
 - d) When dose is eliminated, automatically de-escalate the dose to the next lower level. When the lowest dose is eliminated, stop the study for safety. In this case, no dose should be selected as the MTD.
 - e) If none of the actions (i.e., escalation, de-escalation or elimination) is triggered, treat the new patients at the current dose.
 - f) If the current dose is the lowest dose and the rule indicates dose de-escalation, treat the new patients at the lowest dose unless the number of DLTs reaches the elimination boundary, at which point terminate the study for safety.
 - g) If the current dose is the highest dose and the rule indicates dose-escalation, treat the new patients at the highest dose.
- h) Repeat step 2 until the maximum sample size of 25 is reached or stop Part A of the study if the number of patients treated at the current dose reaches 12.

Figure 10–1 BOIN Design

* DLT rate =
$$\frac{\text{Total number of patients who experienced DLT at the current dose}}{\text{Total number of patients treated at the current dose}}$$

Abbreviations: DLT = Dose-limiting toxicity; MTD = Maximal tolerated dose

After the study is completed, the MTD based on isotonic regression as specified in [Liu and Yuan, 2015](#) is selected (the MTD for which the isotonic estimate of the toxicity rate is closest to the target toxicity rate. If there are ties, the higher dose level is selected when the isotonic estimate is lower than the target toxicity rate and the lower dose level is selected when the isotonic estimate is greater than or equal to the target toxicity rate). [Table 10-2](#) below provides the decision rules to be utilized during the dose-escalation period.

Table 10-2 Dose-Escalation/De-Escalation Decision Rules for the BOIN Design

Actions	The number of patients treated at the current dose											
	1	2	3	4	5	6	7	8	9	10	11	12
Escalate if number of DLT ≤ 0.236	0	0	0	0	1	1	1	1	2	2	2	2
De-escalate if number of DLT ≥ 0.359	1	1	2	2	2	3	3	3	4	4	4	5
Eliminate if number of DLT	NA	NA	3	3	4	4	5	5	5	6	6	7

Abbreviations: BOIN = Bayesian optimal interval; DLT = Dose-limiting toxicity; NA = Not applicable

As of October 29, 2021, 13 evaluable patients have been treated at DL1 to DL5, as shown in [Table 10-3](#) below. PK and PD data show that DL5 has reached the range of therapeutically effective dose. To reduce the chance of exposing patients to higher doses that may yield no additional benefit, amendment is made in Protocol V6.0 to remove DL8 from dose escalation. Accordingly, the maximum sample size in the BOIN is adjusted from 27 to 25.

Table 10-3 Observed Data as of October 29, 2021.

Dose level (DL)	DL1	DL2	DL3	DL4	DL5	DL6	DL7	DL8

10.3.2 Part A-2 (Optional): PD Expansion

The primary objective of the optional Part A-2 is to better understand the exposure-dependent PD/dose response relationship. PD data will be combined across Part A and Part A-2 and summarized using descriptive statistics. If appropriate, the PD/dose relationship may be modelled. The shape of the dose response curve will be identified after plotting the data.

10.3.3 Part B - Clinical Activity Monitoring Using BOP2 Design

The efficacy endpoint is monitored using the BOP2 design (Zhou et al., 2017) in all Part B cohorts except for Cohort B5 (Section 10.6.2.1). Specifically, let n denote the interim sample size and N denote the maximum sample size. Let p_{eff} denote the probability of clinical activity (response rate) and define the null hypothesis $H_0: p_{eff} \leq 0.05$, representing that the treatment is ineffectual. The patient enrollment will be stopped and claimed that the treatment is not promising if:

$$Pr(p_{eff} > 0.05 | data) < \lambda \left(\frac{n}{N}\right)^\alpha$$

Where $\lambda=0.87$ and $\alpha=0.62$ are design parameters optimized to minimize the chance of incorrectly claiming that an efficacious treatment is not promising (i.e., type II error) under the alternative hypothesis $H_1: p_{eff} = 0.2$, while controlling the type I error rate at 0.1 (i.e., the chance of incorrectly claiming that an ineffectual treatment is promising is no more than 10%). Assuming a $\beta(0.05, 0.95)$ prior distribution for p_{eff} , and a maximum of 40 patients per cohort, the above decision rule corresponds to the following stopping boundaries and yields a statistical power of 0.9152 under H_1 :

Table 10-6 Optimized Stopping Boundaries for BOP2 Design

Number of patients treated	Stop if # ORR \leq
25	1
40	4

Abbreviations: BOP2 = Bayesian optimal phase II; ORR = Objective response rate.

The interim analysis will be performed when the number of enrolled patients reaches 25. In this situation, the null hypothesis will be rejected if the number of responses is greater than 1; otherwise it is concluded that the treatment is not promising (Table 10-6). The go/no-go criteria are non-binding though, in particular as an ORR of 10% in the patient population assessed may already be considered a clinically meaningful result by the Sponsor. Futility analyses will be done based on availability of 12 weeks data. The data monitoring committee (DMC), consisting of Sponsor representatives will determine whether a cohort shall be stopped or continued after the interim analysis.

The operating characteristics of the design based on 10,000 simulations using shiny app “BOP2” published by MD Anderson Software are presented in [Table 10-7](#).

Stratification factors will be applied to Part B enrollment.

Table 10-7 Operating Characteristics

Response rate	Early stopping (%)	Claim promising (%)	Sample size
0.01	97.42	0	25.4
0.05	64.24	4.50	30.4
0.10	27.12	35.90	35.9
0.15	9.31	72.22	36.6
0.20	2.74	91.52	39.6
0.25	0.7	99.03	39.9
0.30	0.16	99.64	40
0.35	0.03	99.94	40
0.40	0.01	99.99	40
0.45	0	100	40

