In case (a) cohort is not stopped for futility after the interim analysis, enrollment continues until 40 patients per cohort have been enrolled and treated. A final analysis will then be conducted after initial response data (i.e., based on availability of 12-week data) for the total (maximum) of 40 patients for a given cohort is available. Part A study data discussed with SMC on 23 May 2022 demonstrated the development of treatment-emergent anti-drug-antibodies (ADAs) in a relevant fraction of patients dosed at 24mg-240mg. These ADAs were typically associated with rapid elimination of NM21-1480 from the circulation and loss of exposure. However, PK, PD, receptor occupancy and clinical activity data available for the 800mg dose level indicated that at this dose, the issue of loss of exposure was no longer present while full pharmacodynamic activity was

maintained, a phenomenon described for other checkpoint inhibitors (i.e. atezolizumab) at higher doses as well. As such, the SMC agreed with the Sponsor to further study the 800mg dose level as the presumptive RP2D, applying a biweekly dosing interval in Part B of the study.

For Cohort B5, an interim analysis will be performed after a minimum of 60 patients have been enrolled. At this point recruitment will be paused, the accumulated data analysed and regulatory authorities consulted. At the interim analysis the cohort will be regarded as futile (non-binding) if the probability of observing a difference in estimated effects between control and treatment of at least 15% is less than 0.1. However, as with the other cohorts, decisions at the interim point will be taken based on clinical and regulatory input and not formal statistical testing.

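### Protocol 10.3.3 says H0 is rejected with more than 1 response in 25, but the design it describes makes that count a signal to continue to 40, not a rejection

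*Protocol*

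**What the plan says.** Section 10.3.3 of the protocol sets H0 as a response rate of at most 0.05 and H1 as 0.20, with at most 40 patients per cohort. The monitoring rule is introduced with "The patient enrollment will be stopped and claimed that the treatment is not promising if" the posterior probability that the rate exceeds 0.05 falls below λ(n/N)^α, with λ = 0.87 and α = 0.62. These parameters are said to be chosen while "controlling the type I error rate at 0.1", and the rule "yields a statistical power of 0.9152" under H1.

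Table 10-6, headed "Optimized Stopping Boundaries for BOP2 Design", has two rows: stop with 1 or fewer responses in 25, and with 4 or fewer in 40.

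The paragraph after the table describes the 25-patient interim and says "the null hypothesis will be rejected if the number of responses is greater than 1"; otherwise the treatment is called not promising. It then adds: "The go/no-go criteria are non-binding though".

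Section 7.2.5.4 says that if a cohort is not stopped at the interim, "enrollment continues until 40 patients per cohort have been enrolled and treated", and "A final analysis will then be conducted after initial response data" are available for those patients. Section 10.2 also places a final analysis at 40, and Section 10.7 has cohorts either stopped early for futility or continued to 40.

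**The concern.** The sentence ties rejection of H0 to the look at 25. Nothing else in the design does so: the formula has no early-success arm, and a boundary at 40 would serve no purpose if H0 had already been rejected at 25. This is also the only place in Section 10.3.3 that says in words when H0 is rejected. Table 10-6 gives only stopping counts, so the success criterion of 5 or more in 40 has to be inferred. Anyone who took the sentence as the decision rule would be using a criterion that does not deliver the error rate and power quoted for the design.

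**Working it through.** **Inputs** (all from Section 10.3.3): null rate 0.05, alternative 0.20, looks at n = 25 and N = 40, prior Beta(0.05, 0.95), λ = 0.87, α = 0.62.

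**1. Reproduce the boundaries.** After x responses in n patients the posterior is Beta(0.05 + x, 0.95 + n − x). Stop if Pr(p > 0.05) is below 0.87 × (n/40)^0.62.

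| n | Cut-off | Largest x that stops | Smallest x that passes |
|---|---|---|---|
| 25 | 0.87 × 0.625^0.62 = 0.650 | x = 1: 0.296 | x = 2: 0.658 |
| 40 | 0.870 | x = 4: 0.868 | x = 5: 0.955 |

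Both rows of Table 10-6 are confirmed. Two responses in 25 give 0.658, which just clears the interim cut-off but is well short of the final 0.87.

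**2. Reproduce the stated power.** Under the two-stage rule, the probability of claiming promise is the sum over x ≥ 2 of P(X25 = x) × P(X15 ≥ 5 − x), with exact binomial terms.

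- At 0.20: 91.52%, the protocol's figure.
- At 0.05: 4.59% (Table 10-7 prints 4.50%), inside the 10% limit.

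**3. Apply the sentence literally.** Reject if X25 ≥ 2.

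- At 0.05: 1 − 0.95^25 − 25 × 0.05 × 0.95^24 = 1 − 0.6424 = 35.76%.
- At 0.20: 1 − 0.0274 = 97.26%.

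Table 10-7 itself rules this reading out. At 0.05 it prints 64.24% early stopping. If passing the interim were rejection, the claim-promising entry would have to be 100 − 64.24 = 35.76%, not 4.50%.

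**4. Follow the cohorts that pass.** At a true rate of 5%, 35.76% pass the interim and 4.59% finish with 5 or more of 40. So 4.59/35.76 = 12.8% of those passing end as promising, and about 31.2% of all such cohorts pass the interim but fail at 40. The sentence would count every one of these as a rejection.

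**5. Allow for a non-binding interim.** If the look at 25 is ignored and only 5 or more of 40 is applied, type I error is 4.80% and power 92.4%. The 10% limit still holds.

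**6. Side check of Table 10-7.** Exact values match 27 of the 30 cells to the printed precision: all 10 for early stopping, 8 of 10 for claim promising and 9 of 10 for sample size. The three that differ are:

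- Sample size at 0.15: printed 36.6. The row's own early-stopping rate gives 25 + 15 × (1 − 0.0931) = 38.6. A mean of 36.6 would need (40 − 36.6)/15 = 22.7% early stopping, against 9.31%.
- Claim promising at 0.25: printed 99.03, exact 98.03. With 10,000 simulations the standard error is √(0.9803 × 0.0197/10,000), about 0.14 points, so simulation error does not explain a full point.
- Claim promising at 0.05: printed 4.50, exact 4.59. The 0.09-point gap is within a standard error of √(0.045 × 0.955/10,000), about 0.21 points.

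**The case against.** The best defence is that the documents already resolve the matter. The sentence cites a table of stopping boundaries with a second row at 40, the sentences after it speak of futility and of stopping or continuing, and no procedure anywhere declares success at 25. On that view 35.8% is the error rate of a rule nobody would apply, and the go/no-go criteria are non-binding in any case. All of this is right about intent and limits the weight of the point. It does not make the sentence correct. Freedom to depart from a go/no-go criterion is not a definition of when H0 is rejected.

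It is also fair to say that nothing was affected. SAP Section 6 reports 5, 5 and 10 patients in B1, B7 and B8 and none in the other Part B cohorts, SAP 3.1.5 provides no hypothesis testing, and SAP 5.1 provides no interim analysis.

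On Table 10-7, the 4.50 entry is compatible with simulation error, and any of the three entries could be a typing or text-extraction slip. They are cells to check, not established errors. The 4.50 is still worth a look, because almost every other cell equals the exact value to the printed precision instead of scattering as simulated values would.

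Finally, a repair should not imply that only the interim is non-binding. The protocol applies that label to the criteria generally and cites a 10% response rate as possibly meaningful. That is 4 of 40, exactly the final stopping boundary.

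**Conclusion.** The sentence is wrong as written, and the point is minor. Passing the 25-patient look means continue; H0 is rejected only with 5 or more responses in 40. The stated boundaries and the 0.9152 power reproduce under that rule and not under the sentence. The literal figures of 35.8% and 97.3% describe a hypothetical rule, not the design's error rate. They assume independent binomial responses and complete data at each look. No boundary, sample size, power figure or trial result is put in doubt. Confidence is high on the wording. On the Table 10-7 cells it is limited to the mismatch with exact values.

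**What to change.** Replace the sentence in Section 10.3.3 with wording such as: *At the interim, 1 or fewer responses in 25 suggests stopping for futility (non-binding); with 2 or more, enrolment continues to 40, and H0 is rejected only if 5 or more of 40 respond.* Keep the separate statement that the go/no-go criteria are non-binding, so that it continues to cover the final boundary as well.

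Check three Table 10-7 entries against the original PDF and the BOP2 software output, and correct them only if confirmed: 36.6 in the 0.15 row, 99.03 in the 0.25 row and 4.50 in the 0.05 row.

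The cost is one sentence and a short table check, with no change to data, sample size or any decision.

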10.4 Statistical Analyses Sets

10.4.1 Safety Set

The safety set (SS) consists of all patients who receive at least 1 dose of study drug. Unless otherwise specified, the SS will be the default analysis set used for all analyses.

10.4.2 Dose-Determining Set

The dose-determining set includes all Safety Run-in patients from the SS of Part A who either completed the minimum exposure requirement and have sufficient safety evaluations or experienced a DLT. Patients will be considered to have met the minimum exposure requirement if they received at least 80% of either originally-assigned dose within the first cycle of dosing (i.e., 80% of either the dose administered for Cycle 1/Day 1 [C1D1] or Cycle 1/Day 15 [C1D15]). The length of the DLT evaluation period is 28 days.

Patients who do not experience a DLT during the first cycle will be considered to have sufficient safety evaluations if they have been observed for ≥ 28 days following the first dose, and are considered by both the Sponsor and Investigators to have enough safety data to conclude that a DLT did not occur.

10.4.3 Pharmacokinetic Set

The PK set will consist of all patients who receive at least 1 dose of NM21-1480 and have at least 1 post-dose PK blood collection with associated bioanalytical results. The PK set will be used for summaries and listings of PK data.

10.4.4 Efficacy Analysis Set

Consists of all patients who received at least one dose of study drug and have measurable baseline disease. The Efficacy Analysis Set will be the primary analysis set for efficacy in this study.

For Part B, patients who are still on treatment at the time of data cut-off, but have not yet reached the first post-baseline tumor assessment, will be excluded.

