- w. Bone scans at baseline or subsequent visits will be performed only if clinically indicated. If required, subsequent bone scans should ONLY be repeated every other assessment cycle (i.e., at Weeks 16, 32, etc., in Part A; and at Weeks 12, 24, 40, etc., for Part B) and a single scan at Follow-up Visit in accordance with footnote "v" unless the investigator suspects progression of disease in bone or in case complete response is identified in target disease.
- x. Blood tests are to be tumor-specific (e.g., CEA and CA 19-9 for colorectal and pancreatic cancer, respectively). In case of uncertainty, use of a blood test should be discussed with the Medical Monitor.
- y. Tumor response status will be assessed by the Investigators using RECIST 1.1 *only* (Parts A and A-2), or RECIST1.1 and iRECIST (Part B). Response assessments must be performed by the Investigator every 8 weeks (Parts A), or every 6 weeks during the first 24 weeks the patient is on treatment and every 8 weeks thereafter (Part A-2 and Part B), to document eligibility to remain on treatment with study drug (see also footnote c).
- z. All patients who discontinue from the study within 70 days after the administration of the last dose of study drug should be followed until resolution and/or stabilization of any study TRAE and of those AE(s) that led to the discontinuation, and should be monitored for 70 days following the last dose of NM21-1480 for the occurrence of study TRAE. These patients should complete Follow-up Visits 1 and 2 unless the patient begins a new therapy.
 - aa. For all Follow-up periods beyond 70 days from the last dose of study drug, only study treatment-related SAEs or late-occurring irAEs should be reported.
 - bb. For Cohort B3 only: The screening process is to be conducted in 2 subsequent steps. Following signature of the ICF, PD-L1 expression scoring on tumor cells needs to be conducted either based on archival or fresh biopsy material from the TME and conducted centrally using a Sponsor-approved PD-L1 assay prior to entering the formal 28-day screening period. Only upon determination of a PD-L1 tumor cell expression score qualifying for study inclusion, the remaining eligibility criteria will be assessed.
 - cc. For Part A (Cycle 1 *only*), the site is encouraged to call the patient approximately one week after the Day 15 / Week 3 dosing event in order to learn about any AEs that may have occurred.

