7.2.4 Screen Failures

Screen failures are defined as participants who consent to participate in the clinical study but who do not subsequently receive a minimum of one dose of study drug. A minimal set of screen-failure information is required to ensure transparent reporting of screen-failure participants to meet the Consolidated Standards of Reporting Trials publishing requirements and to respond to queries from regulatory authorities. Minimal information includes demography, screen-failure details, eligibility criteria, and any serious adverse event (SAE).

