8 STUDY TREATMENT

Study treatment is defined as the investigational intervention intended to be administered to the study participant according to the study protocol.

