10.6.2.1 Primary Efficacy Analysis, Cohort B5

For Cohort B5, the primary efficacy endpoint will be central RECIST 1.1 read of ORR. The primary analysis will be performed in the Efficacy Analysis Set using a Bayesian logistic regression model with treatment and (CPS ≥ 1 ; CPS ≥ 20) as a covariates:

$$\text{Logit} (p_i) = \beta_0 + \beta_1 \times \text{treatment} + \beta_2 \times \text{CPS20}$$

The following prior distributions have been assumed:

$\beta_0 \sim N(-1.45, 0.16^2)$, equivalent to a control response rate of 20 ($\pm 4\%$) observed in the KEYNOTE-048 study with pembrolizumab;

$\beta_1 \sim N(0,1)$, vague prior on treatment equivalent to expected treatment difference of 0% (95% confidence interval: -16% to +43%, which corresponds to a $N(0,1)$ prior on logistic scale)

$\beta_2 \sim N(0, 0.1^2)$, vague prior on CPS effect, based on KEYNOTE-048 study with pembrolizumab, where a 0%-3% difference in response was observed across CPS levels.

The Bernoulli likelihood is not conjugate to the normal priors on the regression coefficients and so the posterior distribution of regression coefficients is not known. Let $\beta = (\beta_0, \beta_1, \beta_2)$.

$$\pi(\beta|data) \propto \pi(data|\beta)\pi(\beta)$$

In order to avoid the use of Monte Carlo methods for inference on parameters (and the requirement of large simulations to estimate posteriors with sufficient precision) we fit Laplace approximations to posterior distributions. We approximate $\pi(\beta|data) \approx N(\beta', Var(\beta'))$ where β' is the mode of the posterior distribution of $\pi(\beta|data)$ with $Var(\beta')$ the posterior covariance matrix estimated at this mode.

At the interim analysis, Cohort B5 will be regarded as futile (non-binding) if the probability of observing a difference in estimated effects between control and treatment of at least 15% is less

than 0.1. However, as with the other cohorts, decisions at the interim point will be taken based on clinical and regulatory input and not formal statistical testing. Statistical superiority of the treatment in the final analysis will be concluded if $Pr(\beta_1 > 0 | data)$ is > 0.95 .

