3.2 Analysis Populations

3.2.1 *Safety Set*

The Safety Set (SS) consists of all patients who receive at least 1 dose of study drug (NM21-1480). Unless otherwise specified, the SS will be the default analysis set used for all analyses.

3.2.2 *Efficacy Analysis Set*

The Efficacy Analysis Set (EAS) consists of all patients who received at least one dose of study drug (NM21-1480) and have measurable baseline disease. The Efficacy Analysis Set will be the primary analysis set for efficacy.

. The final analysis will not be performed before all patients have either reached the first post-baseline tumor assessment or discontinued clinical response evaluation.

3.2.3 *Dose-Determining Set*

The dose-determining set includes all Safety Run-in patients from the SS of Part A who either completed the minimum exposure requirement and have sufficient safety evaluations or experienced a DLT. Patients will be considered to have met the minimum exposure requirement if they received at least 80% of either originally-assigned dose within the first cycle of dosing

(i.e., 80% of either the dose administered for Cycle 1/Day 1 [C1D1] or Cycle 1/Day 15 [C1D15]). The length of the DLT evaluation period is 28 days.

Patients who do not experience a DLT during the first cycle will be considered to have sufficient safety evaluations if they have been observed for ≥ 28 days following the first dose and are considered by both the Sponsor and Investigators to have enough safety data to conclude that a DLT did not occur.

3.2.4 *Pharmacokinetic Set*

The PK set will consist of all patients who receive at least 1 dose of NM21-1480 and have at least 1 post-dose PK blood collection with associated bioanalytical results. The PK set will be used for summaries and listings of PK data.

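### As worded, the Efficacy Analysis Set omits the control arm of Cohort B5, although the randomised B5 primary analysis is placed in that set: a drafting defect that affects no reported result

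*Protocol*

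**What the plan says.** Protocol 10.4.4 sets two conditions for the Efficacy Analysis Set: a dose of study drug and measurable disease at baseline ("Consists of all patients who received at least one dose of study drug and have measurable baseline disease"). The Safety Set in 10.4.1, which is the default set for all analyses, carries the same dosing condition.

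For Cohort B5, 10.6.2.1 states: "The primary analysis will be performed in the Efficacy Analysis Set using a Bayesian logistic regression model". The model has a treatment term and a CPS term. Section 7.1 describes B5 as a 2:1 randomisation between a standard-of-care PD-1 inhibitor plus NM21-1480 and the PD-1 inhibitor alone. Section 10.4 defines no randomised set and no set specific to B5.

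SAP 3.2.2 repeats the efficacy definition and names the drug: "all patients who received at least one dose of study drug (NM21-1480) and have measurable baseline disease". SAP 3.2.1 does the same for the Safety Set. Protocol 7.2.4 counts as screen failures those consenting participants "who do not subsequently receive a minimum of one dose of study drug".

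**The concern.** A control patient in B5 never receives NM21-1480. If study drug means NM21-1480, the primary analysis set of the protocol's only randomised cohort contains one arm. The treatment coefficient β1 can then be separated from the intercept β0 only through the informative prior on β0, which comes from an earlier pembrolizumab trial. A randomised comparison becomes a single-arm comparison with a historical rate.

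The loss would be easy to miss. With proper priors on all three coefficients, the model returns a posterior for β1 whether or not any control data are present.

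**Working it through.** **1. What study drug means in the protocol.** There is no formal definition, so usage has to settle it.

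- 7.1.6, Table 7-1 footnote z, refers to the last dose of study drug and, for the same follow-up window, says patients "should be monitored for 70 days following the last dose of NM21-1480".
- 7.2.9 starts from discontinuing study drug and ends by recording the reason for discontinuing NM21-1480.
- 9.2.2 uses the two names interchangeably for the 70-day monitoring period.
- Section 8 on the related term: "Study treatment is defined as the investigational intervention intended to be administered to the study participant according to the study protocol".
- No section extends study drug to the B5 control therapy.

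**2. Applying the sets to B5 as worded.**

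- The plan's own sample size first: 180 / (1 − 0.10) = 200, which matches 10.2.
- Controls under 2:1 allocation: 180 × 1/3 = 60 analysed, and 200 × 1/3 ≈ 67 randomised.
- Controls admitted by 10.4.4: 0 of 60. NM21-1480 patients left: 180 − 60 = 120.
- The same 60 (or 67) are outside the Safety Set and meet 7.2.4.
- Best overall response in 10.6.2.2 counts assessments after the first dose of study drug, a date controls would not have.

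**3. What would replace the controls.** The prior on β0 is N(−1.45, 0.16²). Its centre is a response rate of 1/(1 + e^1.45) = 0.190. Its approximate worth in patients is (1/0.16²) / (0.19 × 0.81) = 39.06 / 0.154 ≈ 254 historical controls.

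**4. Effect on the decision rule.** The 10.6.2.1 model was simulated with its three priors, the Laplace approximation and the rule Pr(β1 > 0 | data) > 0.95, using 100,000 trials per setting and 120 treated patients. The documents do not give every input. The assumptions were half the patients with CPS ≥ 20, no CPS effect, and the true control rates shown.

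| True control rate | Type I error, 60 controls | Type I error, no controls | Power for +15 points, 60 controls | Power for +15 points, no controls |
|---|---|---|---|---|
| 19% | 2.5% | 1.6% | 95.2% | 94.8% |
| 20% | 4.2% | 3.0% | 96.6% | 96.8% |
| 25% | 23.2% | 30.2% | not compared | not compared |

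Near the planning rate the prior does nearly all the work and the controls change little. At a true rate of 25% the error is already high with controls, because of the prior, and it rises by 30.2 − 23.2 = 7.0 points without them.

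**5. The plan's power table.** Table 10-1 gives 90.07% power and 3.91% Type I error at 180 patients. The simulation did not reproduce the table: under the stated rule, power was 94.0% to 96.6% and Type I error 2.5% to 4.4%. Because the inputs behind the table are not fully stated, this does not show it to be wrong. The present point does not depend on it.

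**The case against.** The strongest reply is that the plan leaves no doubt that controls are to be analysed. The model has a treatment covariate, 10.2 powers 180 patients at 2:1, and 9.1.1 has a central reader blinded to B5 treatment assignment. The synopsis has the safety committee compare run-in safety with the anti-PD-1 arm. The footnotes exempting B5 controls (Table 7-1 footnote ii, Table 7-3 footnote j) cover PK and ADA sampling only. All of this stands. It shows that the set definition conflicts with a clear intention, and nothing supports inferring that the sponsor planned to analyse B5 without its comparator.

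A second reply is that study drug may be broader than NM21-1480. The PK Set (10.4.3) names NM21-1480 while the other sets do not, and the causality section (9.2.4.2) mentions product information for marketed products. The SAP's parenthesis is also weak evidence on B5, since that SAP already records an empty B5 (section 6) and no randomisation (2.5.2). These points make the term less than watertight. They do not outweigh the protocol's repeated use of it for NM21-1480.

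A reader might also infer that the set drops every randomised patient without a first scan. It does not. Section 10.4.4 excludes only Part B patients still on treatment at data cut-off who have not reached the first post-baseline assessment. Patients who stop before a scan stay in: 10.6.2.2 classes them as not evaluable, 10.6.2.3 divides by all patients, and SAP 3.1.7 treats them as non-responders. SAP 3.2.2 omits the cut-off exclusion and has the final analysis wait.

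Finally, a set requiring a dose of any assigned treatment is a common choice for response rate in an open-label early-phase cohort, and it too would restore the controls. The measurable-disease condition removes no eligible patient, because inclusion criterion 8 already requires it.

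**Conclusion.** The point holds as a contradiction in wording. Read literally, 10.4.4 removes all B5 controls (about 60 of 180 analysed, 67 of 200 randomised) from the analysis that 10.6.2.1 assigns to it. The treatment effect is then identified only against the historical prior on β0. This rests on study drug meaning NM21-1480, which is supported by usage and by the SAP but not by a formal protocol definition.

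The harm in principle is the loss of the concurrent comparison and of some protection if the historical rate is wrong. A reader might infer a loss of power or a general inflation of error. The simulations, under their stated assumptions, show neither at 19% to 20%, and much of the inflation at 25% belongs to the prior.

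No reported result is affected. B5 enrolled nobody (SAP 6), the trial closed early (SAP 4) and no hypothesis testing is planned (SAP 3.1.5). Priority is therefore low: correct it before B5 is opened or its text is reused.

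**What to change.** For Cohort B5 only:

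- 10.4.4: define the primary efficacy set as all randomised patients with measurable baseline disease, analysed by assigned arm.
- 10.4.1: define the safety set as all patients who received any assigned B5 treatment.
- 7.2.4: reword so that a randomised control patient is not a screen failure.
- 10.6.2.2: start the best-overall-response clock at randomisation or at the first dose of any assigned treatment.

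Carry the same definitions into SAP 3.2.1 and 3.2.2 if B5 is ever opened. The cost is wording alone. The planned 60 + 120 = 180 patients are restored to the analysis, with no change to the sample size, model or decision rule, and nothing has to be re-analysed.
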